10.43 Expedited Reporting by Investigator to SOBI AB

The research staff must inform Swedish Orphan Biovitrum (SOBI) in writing using a SOBI SAE or a MEDWATCH 3500A form of any SAE. The written report must be completed and supplied to SOBI by e-mail or facsimile within 24 hours/1 business day. The initial report must be as complete as possible, including an assessment of the causal relationship between the event and the investigational product(s), if available. Information not available at the time of the initial report (e.g., an end date for the adverse event or laboratory values received after the report) must be documented on a follow-up report. A final report to document resolution of the SAE is required. A copy of the email transmission of the SAE report to SOBI [REDACTED] should be attached to the SAE and retained with the patient records.

SOBI Safety Reporting contact information:

Drug Safety Swedish Orphan Biovitrum

[REDACTED]

The reporting of serious adverse events to SOBi does not relieve the sponsor from other regulatory reporting responsibilities.

SOBi Safety Reporting contact information:

Fax: [REDACTED]

10.5 Other Required Reporting

10.51 Persistent or Significant Disabilities/Incapacities

Any AE that results in persistent or significant incapacity or substantial disruption of the ability to conduct normal life functions (formerly referred to as disabilities), congenital abnormalities or birth defects, must be reported immediately if they occur at any time following treatment with an agent under an IND/IDE since they are considered to be a serious AE and must be reported to the sponsor as specified in 21 CFR 312.64(b).

10.52 Death

Any death occurring within 30 days of the last dose, regardless of attribution to an agent/intervention under an IND/IDE requires expedited reporting within 24-hours.

Any death occurring greater than 30 days with an attribution of possible, probable, or definite to an agent/intervention under an IND/IDE requires expedited reporting within 24-hours.

Reportable categories of Death:

- Death attributable to a CTCAE term.
- Death Neonatal: A disorder characterized by cessation of life during the first 28 days of life.
- Death NOS: A cessation of life that cannot be attributed to a CTCAE term associated with Grade 5.
- Sudden death NOS: A sudden (defined as instant or within one hour of the onset of symptoms) or an unobserved cessation of life that cannot be attributed to a CTCAE term associated with Grade 5.
- Death due to progressive disease should be reported as **Grade 5 “Neoplasms benign, malignant and unspecified (incl cysts and polyps) – Other (Progressive Disease)”** under the system organ class (SOC) of the same name. Evidence that the death was a manifestation of underlying disease (e.g., radiological changes suggesting tumor growth or progression: clinical deterioration associated with a disease process) should be submitted.

10.53 Secondary Malignancy

A **secondary malignancy** is a cancer caused by treatment for a previous malignancy (e.g., treatment with investigational agent/intervention, radiation or chemotherapy). A secondary malignancy is not considered a metastasis of the initial neoplasm.

All secondary malignancies that occur following treatment with an agent under an IND/IDE must be reported. Three options are available to describe the event:

- Leukemia secondary to oncology chemotherapy (e.g., Acute Myelocytic Leukemia [AML])
- Myelodysplastic syndrome (MDS)
- Treatment-related secondary malignancy

Any malignancy possibly related to cancer treatment (including AML/MDS) should also be reported via the routine reporting mechanisms outlined in each protocol.

10.54 Second Malignancy

A second malignancy is one unrelated to the treatment of a prior malignancy (and is NOT a metastasis from the initial malignancy). Second malignancies require ONLY routine reporting.

10.55 Pregnancy

Females of reproductive potential must adhere to scheduled pregnancy testing as required in the Revlimid REMS™ program.

Pregnancies and suspected pregnancies (including a positive pregnancy test regardless of age or disease state) of a female subject occurring while the subject is on lenalidomide, or within 28 days of the subject's last dose of lenalidomide, are considered immediately reportable events. Lenalidomide is to be discontinued immediately. The pregnancy, suspected pregnancy, or positive pregnancy test must be reported to Celgene Drug Safety immediately by facsimile or email using the Pregnancy Initial Report Form. The female subject should be referred to an obstetrician-gynecologist, preferably one experienced in reproductive toxicity for further evaluation and counseling.

The Investigator will follow the female subject until completion of the pregnancy, and must notify Celgene Drug Safety immediately about the outcome of the pregnancy (either normal or abnormal outcome) using the Pregnancy Follow-up Report Form. If the outcome of the pregnancy was abnormal (e.g., spontaneous or therapeutic abortion), the Investigator should report the abnormal outcome as an AE. If the abnormal outcome meets any of the serious criteria, it must be reported as an SAE to Celgene Drug Safety immediately by facsimile, or other appropriate method, within 24 hours of the Investigator's knowledge of the event using the SAE Report Form.

If the outcome of the pregnancy was abnormal (e.g., spontaneous or therapeutic abortion), the investigator should report the abnormal outcome as an AE. If the abnormal outcome meets any of the serious criteria, it must be reported as an SAE to Celgene Drug Safety immediately by facsimile, or other appropriate method, within 24 hours of the investigator's knowledge of the event using the SAE report form, or approved equivalent form.

Pregnancy reporting is also required for SOBi according to the same guidelines.

10.551 Neonatal deaths

All neonatal deaths that occur within 28 days of birth should be reported, without regard to causality, as SAEs. In addition, any infant death after 28 days that the Investigator suspects is related to the in utero exposure to the IP should also be reported to Celgene Drug Safety immediately by facsimile, or other appropriate method, within 24 hours of the Investigator's knowledge of the event using the SAE Report Form.

10.552 Male Subjects

10.56 Overdose

Overdose, as defined for this protocol, refers to lenalidomide and anakinra dosing only.

On a per dose basis, an overdose is defined as the following amount over the protocol-specified dose of lenalidomide or anakinra assigned to a given patient, regardless of any associated adverse events or sequelae.

Method of administration	Amount that constitutes overdose
PO	any amount over the protocol-specified dose
IV	10% over the protocol-specified dose
SC	10% over the protocol-specified dose

On a schedule or frequency basis, an overdose is defined as anything more frequent than the protocol required schedule or frequency.

On an infusion rate basis, an overdose is defined as any rate faster than the protocol-specified rate. Complete data about drug administration, including any overdose, regardless of whether the overdose was accidental or intentional, should be reported in the case report form.

10.561 Celgene Drug Safety Contact Information:

Celgene Corporation
Global Drug Safety and Risk Management
[name]

[Redacted]

10.562 SOBi Drug Safety Contact Information:
SOBi Safety Reporting contact information:

[Redacted]

10.6 Required Routine Reporting

Adverse events to be graded at each evaluation and pretreatment symptoms/conditions to be evaluated at baseline per the CTCAE v4.0 grading unless otherwise stated in the table below:

SYSTEM ORGAN CLASS	Adverse event/Symptoms	Baseline	Each evaluation
Investigations	Creatinine increased	X	X
	Neutrophil count decreased	X	X
	Platelet count decreased	X	X
	Lymphocyte count decreased	X	X
	White blood cell decreased	X	X
	Anemia	X	X
General disorders and administration site conditions	Fatigue	X	X
	Injection site reaction		X
Gastrointestinal Disorders	Nausea	X	X
	Vomiting	X	X
	Diarrhea		X
	Constipation		X
	Number of stools	X	
Renal and urinary disorders	Chronic kidney disease (decreased creatinine clearance)	X	X
Skin and subcutaneous tissue disorders	Rash, maculopapular	X	X
Nervous system disorders	Peripheral sensory neuropathy	X	X
Constitutional Symptoms	Insomnia	X	X
Vascular Disorders	Thromboembolic event	X	X

10.61 Submit via appropriate MCCC Case Report Forms (i.e., paper or electronic, as applicable) the following AEs experienced by a patient and not specified in Section 10.6 (above):

10.611 Grade 2 AEs deemed *possibly, probably, or definitely* related to the study treatment or procedure.

10.612 Grade 3 and 4 AEs regardless of attribution to the study treatment or procedure.

10.613 Grade 5 AEs (Deaths)

10.6131 Any death within 30 days of the patient's last study treatment or procedure regardless of attribution to the study treatment or procedure.

- 10.6132 Any death more than 30 days after the patient's last study treatment or procedure that is felt to be at least possibly treatment related must also be submitted as a Grade 5 AE, with a CTCAE type and attribution assigned.
- 10.62 Refer to the instructions in the Forms Packet (or electronic data entry screens, as applicable) regarding the submission of late occurring AEs following completion of the Active Monitoring Phase (i.e., compliance with Test Schedule in [Section 4.0](#)).
- 10.7 All serious adverse events (SAEs) will be followed until resolution or death.

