8.0 Dosage Modification Based on Adverse Events

Strictly follow the modifications in this table for the first **two** cycles, until individual treatment tolerance can be ascertained. Thereafter, these modifications should be regarded as guidelines to produce mild-to-moderate, but not debilitating, side effects. If multiple adverse events are seen, administer dose based on greatest reduction required for any single adverse event observed. Reductions or increases apply to treatment given in the preceding cycle and are based on adverse events observed since the prior dose.

ALERT: *ADR reporting may be required for some adverse events (See Section 10)*

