8.3 Dose Modifications of Anakinra/Placebo during a Cycle of Therapy

Dose reductions of one drug and not the other may be done at the investigators discretion based on attribution of adverse events except neutropenia in which lenalidomide should be decreased first before anakinra.

CTCAE System/organ/Class (SOC)	ADVERSE EVENT	AGENT	ACTION ** (each cycle)
Blood and lymphatic system disorders	Febrile Neutropenia \geq Grade 3	Anakinra/ Placebo	For ANC <1000, omit anakinra/placebo until ANC \geq 1500. Then restart anakinra or placebo with the dose reduced one dose level.
Infections and Infestations	Infection/Febrile Neutropenia \geq Grade 2		Omit until infection resolved; then restart at same dose
	Infection/Febrile Neutropenia \geq Grade 3		Omit until infection resolved; then restart anakinra or placebo with the dose reduced one dose level
Other non-hematologic adverse event	Any adverse event \geq Grade 3		Omit until toxicity reduces to \leq grade 2; then restart anakinra or placebo with the dose reduced one dose level

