Drugs that affect the immune system by blocking TNF have been associated with an increased risk of reactivation of latent tuberculosis (TB). It is possible that taking drugs such as anakinra that blocks IL-1 increases the risk of TB or other atypical or opportunistic infections. (Section 5.1 of the USPI)

Hypersensitivity reactions – Hypersensitivity reactions, including anaphylactic reactions and angioedema have been reported with anakinra. If a severe hypersensitivity reaction occurs, administration of anakinra should be discontinued and appropriate therapy initiated. (Section 5.3 of the USPI)

Immunosuppression – The impact of treatment with anakinra on active and / or chronic infections and the development of malignancies is not known. (Section 5.4 of the USPI)

15.37 Known potential toxicities:

>10% of patients:

Local: Injection site reaction (majority mild, typically lasting 14-28 days, characterized by erythema, ecchymosis, inflammation, and pain). Infection (Upper respiratory infections were 14% in the combined studies while serious infections were only 2%).

1% to 10% of patients: Hematologic: neutropenia

Miscellaneous: Headache, Immunogenicity to Anakinra.

<1% of patients (limited to important or life-threatening):

Hypersensitivity reactions (including anaphylaxis, angioedema, pruritus, rash, urticarial)

15.38 Drug procurement: As of October 31, 2018. Available from commercial supply. Note: Previously provided by SOBI, AB.

15.39 Nursing Guidelines:

- 15.391 Instruct patients on self-administration of anakinra and monitoring of injection sites. Be sure to instruct patient on rotating injection sites - injection sites should be at least 1 inch away from previous injections.
- 15.392 Allow solution to warm to room temperature over 60-90 minutes. Do not shake.
- 15.393 Patients should not receive live vaccines while on agent.
- 15.394 Instruct patient about injection site reactions which can last anywhere from 14-28 days. Instruct patient to contact PI if they have concerns about injection site reactions.
- 15.395 Warn patients of infection risk. Instruct patients to report any fever, or other signs/symptoms of infection to the study team.
- 15.396 Patients may experience headache. Treat symptomatically and monitor for effectiveness.
- 15.397 Although less common, gastrointestinal side effects (diarrhea and nausea), may be seen. Treat symptomatically and monitor for effectiveness.

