16.23 Analysis Plans

All the relevant results pertaining to toxicity, MTD, response, timed endpoints and laboratory correlates will be examined in an exploratory and hypothesis-generating fashion. The small sample size and the heterogeneous patient population associated with phase I studies restricts the generalizability of the results. Any notable statistical result should only be viewed as preliminary evidence for further study in Phase II trials rather than a definitive finding in and of itself. Data will continue to be collected on patients as long as they are trial participants.

16.231 Adverse Events Profile

The number and severity of all adverse events (overall and by dose-level) will be tabulated and summarized in this patient population. The Grade 3+ adverse events will also be described and summarized in a similar fashion. This will provide an indication of the level of tolerance for this treatment combination in this patient group.

16.232 Toxicity Profile

The term toxicity is defined as adverse events that are classified as either possibly, probably, or definitely related to study treatment. Non-hematologic toxicities will be evaluated via the ordinal CTC standard toxicity grading. Hematologic toxicity measures of thrombocytopenia, neutropenia, and leukopenia will be assessed using continuous variables as the outcome measures (primarily nadir) as well as categorization via CTC standard toxicity grading.

Overall toxicity incidence as well as toxicity profiles by dose level, patient and tumor site will be explored and summarized. Frequency distributions, graphical techniques and other descriptive measures will form the basis of these analyses.

16.233 Response Profile

A response is defined to be a sCR, CR, VGPR, or PR noted as the objective status. Response will be evaluated using all cycles of treatment. All patients meeting the eligibility criteria who have signed

a consent form and have begun treatment will be evaluable for response.

Responses will be summarized by simple descriptive summary statistics delineating complete and partial responses as well as stable and progressive disease in this patient population.

Phase II Portion

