The primary goal of this trial is to compare the time to progression of the standard treatment arm (Arm A) to the experimental arm (Arm B). We will conduct a randomized trial comparing the experimental arm against the standard treatment arm. We will enter 45 evaluable patients to each arm of the study using a 1:1 randomization scheme (Pocock et al, 1975). The stratification factors that will be used are listed in Section 5.0. The primary analysis will be a comparison of Arm A to Arm B using a one-sided log-rank test between the two Kaplan-Meier curves. This final analysis will take place after an approximate 24-month accrual period and after 52 total progressions have occurred or the last patient has been followed for at least 2 years (whichever occurs first). Additionally, we assume a constant accrual rate over the course of the study and that we will not have a significant lost to follow-up issue, as historically lost to follow-up rates in Mayo clinic trials have been $< 1\%$. A sample size of 45 evaluable patients per arm (90 total) provides 80% power to detect an improvement in median time to progression from 20 months to 40 months (a hazard ratio of 2.0), using a 1-sided log-rank test at a significance level of 0.05. A final decision regarding the level

of promise for the experimental regimen will take all factors into account including TTP, response rate, OS, adverse events, and other relevant factors. All patients meeting the eligibility criteria who have signed a consent form and have begun treatment will be evaluable for the primary endpoint.

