16.34 Adverse Events

All eligible patients that have initiated treatment will be considered evaluable for assessing adverse event rate(s). The maximum grade for each type of adverse event will be recorded for each patient, and frequency tables will be reviewed to determine patterns. Additionally, the relationship of the adverse event(s) to the study treatment will be taken into consideration.

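### Minor, cheap improvement: infection, one of two anakinra toxicities listed above 10%, is not solicited in Table 10.6, so an unrelated non-serious Grade 2 infection need not be submitted

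*Combined protocol and SAP*

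**What the plan says.** All references are to the combined protocol and SAP.

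- **Labelled risk.** Section 15.37 lists two anakinra toxicities above 10%. One is injection site reaction. The other reads "Infection (Upper respiratory infections were 14% in the combined studies while serious infections were only 2" (per cent).
- **Solicited events.** Table 10.6 marks 17 events for grading at each evaluation. Injection site reaction is included. No infection term or class appears.
- **Unlisted events.** Section 10.61 sets what must be submitted outside the table: under 10.611, "Grade 2 AEs deemed *possibly, probably, or definitely* related to the study treatment or procedure"; under 10.612, Grade 3 and 4 events whatever the attribution; under 10.613, deaths. Grade 1 is not mentioned.
- **Dose rule.** For infection of Grade 2 or higher, Table 8.3 directs for anakinra/placebo: "Omit until infection resolved; then restart at same dose". The row carries no attribution condition. Section 8.0 makes the tables binding for two cycles. After that: "Thereafter, these modifications should be regarded as guidelines to produce mild-to-moderate, but not debilitating, side effects".
- **Analysis.** Section 16.34 states: "The maximum grade for each type of adverse event will be recorded for each patient, and frequency tables will be reviewed to determine patterns". It continues: "Additionally, the relationship of the adverse event(s) to the study treatment will be taken into consideration". Under Section 16.31, the final decision on the level "of promise for the experimental regimen will take all factors into account including TTP, response rate, OS, adverse events, and other relevant factors".

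**The concern.** The protocol solicits one of the experimental drug's two most frequent labelled toxicities and leaves the other to a filter based on the investigator's view of cause. The same protocol regards a Grade 2 infection as reason enough to interrupt the blinded injection. A dose interruption can therefore be on record with no adverse event to explain it.

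The adverse event tables are described as tables of adverse events, with relationship considered in addition. For Grade 2 infection, the required data do not guarantee an all-cause count. A patient whose worst infection was a non-serious Grade 2 judged unrelated may appear to have had no infection of Grade 2 or higher. An event that was never submitted cannot be recovered later from the required forms. What is at stake is the completeness of one descriptive safety count that feeds the overall judgement of the regimen.

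**Working it through.** **Step 1. Is there another route into the required data?** Take a non-serious Grade 2 infection judged unlikely or unrelated.

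| Provision | Covers it? |
|---|---|
| Table 10.6 | No, infection is not listed |
| 10.611 | No, requires at least possible relationship |
| 10.612, 10.613 | No, Grade 3-4 events and deaths |
| 10.4 with 10.11 (expedited events also go into routine data) | No, this brings in infections with hospitalization of 24 hours or more |
| Section 4.0, footnote 9 (late-event call) | No, Grade 3 or higher, serious events and deaths |

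No provision requires it. The Evaluation/Treatment form (18.12) and the diary (Appendix V) may show the omitted doses or a complaint, but neither is an adverse event record.

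**Step 2. What does not depend on it?**

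- Toxicity in the related sense. Section 16.232 says: "The term toxicity is defined as adverse events that are classified as either possibly, probably, or definitely related to study treatment". This stands in the Phase I plan but is the only definition given, so objective 2.22 is largely untouched.
- The infection DLT, which is Grade 4 (7.22).
- The accrual stopping rule, which uses related non-hematologic events of Grade 4 or higher (16.362).

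**Step 3. How large could the shortfall be?** The plan gives no figure to reproduce. It states neither the Grade 2 infection rate nor the share judged related. Inputs:

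- n = 45 evaluable patients per arm (16.12)
- p = share of patients whose worst infection is a non-serious Grade 2; assumed 10% to 30%
- c = share of these judged at least possibly related (capture); assumed 90% to 95%, with 75% and 50% as lower cases

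Missing patients per arm = n × p × (1 − c). In percentage points this is 100 × p × (1 − c). The standard error (SE) of the between-arm difference is √(2p(1 − p)/45).

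| c | p = 10% | p = 20% | p = 30% |
|---|---|---|---|
| 95% | 0.225 (0.5 points) | 0.45 (1.0) | 0.675 (1.5) |
| 90% | 0.45 (1.0) | 0.90 (2.0) | 1.35 (3.0) |
| 75% | 1.125 (2.5) | 2.25 (5.0) | 3.375 (7.5) |
| 50% | 2.25 (5.0) | 4.5 (10.0) | 6.75 (15.0) |
| SE of difference | 6.3 points | 8.4 points | 9.7 points |

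Example at p = 20%: 45 × 0.20 = 9 patients in truth. Recorded: 9 × 0.90 = 8.1 to 9 × 0.95 = 8.55. The exact 95% confidence interval for 9/45 is 9.6% to 34.6%.

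**Step 4. Effect on the comparison.**

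- Equal capture in both arms multiplies the difference by c, so it shrinks by 5% to 10% at c = 95% to 90%. The ratio is unchanged.
- Capture of 95% in one arm and 90% in the other multiplies the ratio by 0.95/0.90 = 1.06 or 0.90/0.95 = 0.95. With equal true rates, the spurious difference is p × 0.05, or 0.5 to 1.5 points.
- Even if all the loss fell in one arm, the points in the table stay below the SE at 75% capture or better. At 50% capture they would exceed it for p = 20% and p = 30%.

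**The case against.** The strongest case against acting is that this is a preference with negligible effect. Filtering unlisted low-grade events by attribution is a uniform rule in Section 10.61, no decision rule uses Grade 2 events, and the size rests wholly on assumed rates. Capture is also likely to be high. The lowest qualifying attribution category in 10.3 is an easy bar to meet, and Section 15.17 lists many common infections as very common with lenalidomide, which both arms receive. All of this stands, and it is why the point is minor. It does not remove the gain: an all-cause count of a main labelled risk for one table entry.

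Three stronger readings are tempting, and the documents do not support them.

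- A reader might infer that unrelated Grade 2 infections cannot reach the database. Section 10.6 sets a minimum, and a site may submit more. The accurate statement is that they need not be submitted.
- A reader might infer that an anakinra excess of mild infection would be hidden. The 14% upper respiratory figure has no comparator. The comparative figure in 15.36 is for serious infection (2% against under 1% on placebo, in rheumatoid arthritis), and serious infections are collected. Phase II is double-blind, so any loss should be mostly similar between arms, and its direction is unknown.
- A reader might infer that the toxicity objective or safety monitoring fails. Step 2 shows otherwise.

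**Conclusion.** The point holds as an optional improvement, not an error. The required data may undercount all-cause Grade 2 infection in the Section 16.34 tables. At an assumed incidence of 10% to 30% and capture of 90% to 95%, the shortfall is about 0.2 to 1.4 patients per arm (0.5 to 3.0 points), less than the sampling error of the between-arm difference (6.3 to 9.7 points). At 20% incidence and 75% capture it is 2.25 patients per arm. Incidence and capture are both assumptions, so calling the shortfall probably small is a judgement resting on the reasons for high capture. The primary analysis does not change either. The gain is prospective: Phase I treatment has ended under Addendum 5, and the Phase II schema leaves the anakinra supply open.

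**What to change.** Before Phase II opens:

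1. In Table 10.6, under the CTCAE class for infections and infestations, add an entry marked at baseline and at each evaluation. Record the specific CTCAE term and grade of any infection of Grade 2 or higher, regardless of attribution. Recording any grade is an alternative, but it brings in Grade 1 events that 10.61 does not now require.
2. Keep the baseline mark. Exclusion 3.22 can be read as covering only infections that need intravenous antibiotics, so a patient may enter with a mild infection that should not be counted as arising on study.
3. In Section 16.34, tabulate infection of Grade 2 or higher and of Grade 3 or higher by arm, pooled across infection terms, both all-cause and at least possibly related. Pooling must be stated, because 10.12 makes each CTCAE term a separate event and 16.34 tabulates by type.

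The cost is low. The evaluations and end-of-cycle telephone calls already exist (7.6), and patients are already asked to report signs of infection (15.395). No visit, sample or design figure changes. The downside is slightly more data entry and higher reported infection rates in both arms.
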